5.7.3 Missing or incomplete data and loss to follow-up

Key strategies for minimizing missing or incomplete data and loss to follow-up for pregnancy registries include activities for registry awareness, recruitment, and retention (of patients and HCPs). Complete details of registry awareness, outreach, and retention efforts will be described in the Recruitment and Retention Plan, and may include the following methods to: 1) increase awareness of the registry by using multiple approaches aimed toward HCPs and patients, such as websites and apps, social media, print media, and scientific conferences; 2) evaluate awareness of the registry periodically; 3) accept data from multiple sources; 4) minimize the burden on HCPs; 5) consistently communicate with HCPs and patients; 6) possibly compensate HCPs; and 7) minimize the burden on patients. Compensation will be considered for patients and/or HCPs, where allowed by local regulations. All activities in this plan will be reviewed on a regular basis and, if needed, changes to the awareness, recruitment, or retention activities or data collection process will be implemented based on the review. The strategies for these activities are described in more detail in Section 5.4.5.

In order to prevent missing data, the following is done:

- Ensuring the primary variables of interest are routinely collected as part of standard-of-care.
- Collecting information via patient reporting, if not collected via HCPs.
- Collecting data elements aligned with study objectives to minimize patient burden.

- Including "not applicable" and "not done" on the CRFs to differentiate from values that are truly unknown.
- Training CC research staff in data collection.
- Planning an interim analysis(es) to characterize enrollment and loss to follow-up to help minimize missing data in the future.
- Checking for missing data patterns and addressing any issues with targeted operational strategies.
- Implementing direct-to-patient strategies to facilitate the capture of patient-reported information.

Should missing data occur, the data will be analyzed as they are recorded in the eCRFs. However, the missing values for data elements will be reported in the annual reports and will be assessed for the likely impact of missing data on the analysis and the pattern of the missing information. Handling of missing data will be described in detail in the SAP.

5.7.4 Analysis sets and groups

5.7.4.1 Baseline descriptive analysis

Patient characteristics are described in Section 5.7.2.1.

Patient disposition characteristics, including summaries for enrolled patients, patients in the analysis set, completers and early withdrawals with the reasons for early discontinuation will be provided. In addition, demographic information (e.g., age, race/ethnicity, BMI), clinical characteristics, including comorbidities and medications, other potential factors that may affect pregnancy outcome, and QUVIVIQ exposure will be described.

5.7.4.2 Analysis of primary and secondary endpoints

The prevalence of major and minor congenital malformations will be calculated using the MACDP convention. If needed for future analyses, minor and major congenital malformations will also be calculated using the EUROCAT convention using the same process. Major malformations will be analyzed separately from minor malformations, with the primary analysis including only adjudicated major congenital malformations. The total prevalence will be calculated by dividing the number of women with any adjudicated cases of each event (observed in live births, fetal deaths, elective or therapeutic terminations, and at any gestational age) by the total number of pregnancies (excluding spontaneous terminations and ectopic or molar pregnancies). The prevalence at birth will be calculated as number of cases observed in live births and stillbirths divided by the total number of births (stillbirths + live births). Data analysis for major congenital malformations will be based on exposure to QUVIVIQ from within 5 half-lives prior to conception through the end of the first trimester.

Confidential

The prevalence of pregnancy complications, including preeclampsia, pregnancy-induced hypertension, gestational diabetes, and preterm labor, will be summarized by dividing the number of pregnant women with that complication by the total number of pregnant women.

The prevalence of spontaneous abortions will be calculated by dividing the number of women with fetal loss occurring before 20 weeks gestation by the total number of pregnant women.

The prevalence of elective and therapeutic abortion will be estimated similarly as separate outcomes.

The prevalence of preterm birth will be calculated by dividing the number of cases by the total number of births (stillbirths + live births). The prevalence of small for gestational age will be calculated by dividing the number of cases by the total number of live births.

For other events of interest occurring in developing neonates and infants, including mortality, hospitalizations for serious illness, growth, and developmental delays, the prevalence will be calculated as the number of cases divided by the total number of live births.

The prevalence of primary and secondary outcome measures will be presented with 97.5% CIs for binomial proportion. The analyses summarized in this section will be performed on the Cohort A and Cohort B.

The maternal, fetal, and infant outcomes of Cohort A will be compared to Cohort B1 (primary analysis), as well as to Cohort B overall and Cohort B2 (secondary analysis). Additionally, the observed prevalence of major congenital malformations of Cohort A and the external comparator cohort(s) will be assessed.

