5.2 Study population

Women with insomnia disorder in a standard-of-care setting, and pregnant at time of enrollment, will be prospectively enrolled prior to any pregnancy outcome. Women with insomnia disorder exposed to QUVIVIQ at any time during pregnancy or within 5 half-lives prior to conception will be assigned to Cohort A. Women with insomnia disorder who have been exposed to non-ORA medications for insomnia during pregnancy or within 5 half-lives of the respective insomnia medication prior to conception (Cohort B1) and women with insomnia who have not been exposed to any insomnia medication during pregnancy and within 5 half-lives of any insomnia medication taken prior to conception (Cohort B2) will comprise the comparator group (Cohort B).

Secondary data sources will be used to evaluate the rate of complications in parallel with external comparator cohort(s) representing the prevalence of birth defects in the general population [see Section 5.4.4]. To reduce bias that may occur if outcome information is known prior to enrollment, pregnant women should be enrolled in the study as soon as their pregnancy is known, prior to any informative prenatal testing (such as maternal serum screening or amniocentesis) where the knowledge of the primary study outcome of their pregnancy would be known – either normal or abnormal), and preferably in the first trimester before 20 weeks gestation.

Women who were exposed to QUVIVIQ during pregnancy or within 5 half-lives prior to conception, but for whom the outcome of pregnancy is known prior to enrollment (retrospective pregnancies), will be enrolled in this study and analyzed in a separate case series.

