5.2.1.1 Eligibility criteria for prospective pregnancies

Inclusion criteria

- Diagnosis of insomnia disorder prior to pregnancy.
- Pregnancy is ongoing and outcome of pregnancy (i.e., pregnancy loss or live birth) is not known.
- One of the following:
 - Woman exposed to QUVIVIQ at any time during the current pregnancy or within 5 half-lives prior to conception.
 - Woman exposed to other, non-ORA medications for insomnia during pregnancy or within 5 half-lives of the respective insomnia medication prior to conception.

Confidential

- Woman unexposed to any insomnia medication during pregnancy and within
 5 half-lives of any insomnia medication taken prior to conception.
- Able and willing to consent to the conditions and requirements of the registry. If the patient is a minor, able and willing to consent/assent according to local regulations.
- Agrees to electronically sign the Release of Medical Information Form permitting the study staff to contact her HCPs (e.g., primary care provider, insomnia specialist, psychiatrist, obstetrician, nurse midwife) and the infant's HCP (e.g., pediatrician) for medical information.

Exclusion criteria

- Exposure to any ORA other than QUVIVIQ (including BELSOMRA® (suvorexant), DAYVIGO® (lemborexant), any ORA newly approved during the study period, or any ORA in pre-market clinical studies) during the current pregnancy or within 5 half-lives of the respective medication prior to conception.
- Woman is currently participating in an interventional study or has taken an investigational product within 3 months prior to conception or during the current pregnancy.

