5.3 Variables

5.3.1 Exposure definition and measures

Exposure information recorded will include start and stop dates, dose, dosing frequency, and reason for discontinuation (if applicable).

The following criteria will be used to assign women to one of the cohorts:

- Cohort A: Exposure to QUVIVIQ at any point during the patient's pregnancy or at any time within 5 half-lives prior to conception.
- Cohort B:
 - Cohort B1: No exposure to QUVIVIQ or any other ORA (including, suvorexant, lemborexant, any ORA newly approved during the study period, or any ORA in pre-marketing clinical studies) but exposure to another insomnia medication [Appendix 3] during pregnancy or within 5 half-lives of the respective medication prior to conception.
 - Cohort B2: No exposure to any insomnia medication during pregnancy and within
 5 half-lives of the insomnia medication taken prior to conception.

Women with retrospective pregnancies will be considered to have been exposed to QUVIVIQ if there is documentation of exposure to QUVIVIQ at any point during the patient's pregnancy or at any time within 5 half-lives prior to conception.

Exposure assessments will not be determined for the external comparator cohort(s), as patient-level data is not available; these cohorts represent the prevalence of birth defects in the general population.

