5.7.4.3 Comparative analyses

Internal comparator analysis

Only prospective pregnancies will be included in the internal comparator analysis. As described in Section 5.7.1.3 in the primary analysis of major congenital malformations, Cohort A will be compared to Cohort B1. In a secondary analysis of major congenital malformations, Cohort A will be compared to Cohort B overall and Cohort B2. All secondary outcome proportions in Cohort A will be compared to Cohort B, as well as separately with Cohorts B1 and B2 using the risk ratio (one-sided 97.5% CIs). The difference in proportions will also be compared to the defined clinical equivalence margin to reject the hypothesis that the rate in Cohort A is higher than in Cohort B1. Also, comparisons may be explored using risk ratios adjusted to relevant covariates through methods such as propensity score weighting, if the sample size is sufficient in subgroups of the covariates. The key covariates of interest that will be considered for adjustment are maternal age, prior history of elective or therapeutic pregnancy termination status, other

Confidential

insomnia treatment exposures, and baseline alcohol, smoking, marijuana, and drug use. Other prior pregnancy and prior infant outcomes will be explored and considered for adjustment at the time of analysis.

The primary and secondary outcomes will be evaluated and described among subgroups of patients defined by key characteristics of interest including maternal age, race/ethnicity, smoking, and exposure to other insomnia medications [see Section 5.7.4.4].

External comparator cohort analysis

Prevalence for major congenital malformations in Cohort A will be assessed in parallel to the prevalence observed in available external comparator cohort(s) representing the background prevalence of birth defects in the general US and EEA population. The MACDP and EUROCAT classification of congenital malformations will be implemented to ensure comparability to US and EEA populations, respectively.

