5.7.4.4 Sensitivity and subgroup analyses

Sensitivity analyses will be performed on both Cohort A and Cohort B if sufficient sample size allows, including but not limited to that which is listed in Table 6.

Table 6 Sensitivity analysis subgroups and outcomes analyzed

Subgroup	Outcome analyzed
Women who have received any prenatal testing that provides knowledge of pregnancy outcome, regardless of findings	Major congenital malformations
Women who have received any prenatal testing that provides knowledge of pregnancy outcome before enrollment, where results are known, regardless of the findings	Major congenital malformations
Women who received any first trimester prenatal screening that provides knowledge of pregnancy outcome before enrollment where result is known to be negative	Major congenital malformations
Women with exposure to QUVIVIQ preconception and in each trimester of exposure ^a	Major congenital malformations
Women with exposure to QUVIVIQ preconception and in each trimester of exposure	Minor congenital malformations
Women with exposure to insomnia medications (Cohorts A and B1) by type (continuous vs intermittent), duration, and dosage of exposure	Major congenital malformations
Women in the primary analysis	Spontaneous abortion occurring before 22 weeks of gestation
Women in primary analysis based on gestational age of enrollment	Spontaneous abortion
Women who did not take known teratogens during pregnancy	Major congenital malformations
Women with clinically confirmed insomnia disorder	Major congenital malformations
Women with exposure to QUVIVIQ and additional medications for insomnia treatment from preconception through end of pregnancy	Major congenital malformations

^a The primary cut point will be the date of conception (LMP + 14 days) to the end of the first trimester (14 weeks gestation), additional sensitivity cut points will include 18 weeks prior to conception through the end of the first trimester, conception date to the end of the pregnancy, 18 weeks prior to conception to the end of pregnancy, second trimester exposure only, and third trimester exposure only.

LMP = last menstrual period.

Full details will be described in the SAP.

Confidential

Subgroup analysis

Both Cohort A and Cohort B (overall and separately for Cohorts B1 and B2) will be summarized and compared for primary and secondary outcomes both overall and by the subgroups of the following parameters, if sufficient sample size allows:

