5.9.1.3 Selection bias

Spontaneous abortions most frequently occur in early pregnancy, likely before the pregnancy is recognized. Even if the pregnancy is recognized and confirmed, it is possible that the pregnancy may not be reported to the study if the loss occurred before enrollment in the study. Not capturing all early pregnancy losses will likely lead to an underestimation of the true early pregnancy loss rate. There is no reason to believe that this study will be differentially impacted by this bias, so even though the spontaneous early losses may be underestimated, the relative rate compared with the other registries should not be affected.

There is potential for channeling bias by label indication due to the severity of insomnia and patient insomnia treatment history. Women with more severe insomnia may be more likely to be prescribed QUVIVIQ compared to women with less severe insomnia histories. Baseline insomnia severity and prior treatments will be captured to assess the degree of confounding by indication.

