Appendix 4 List of exposure windows for secondary outcomes

As detailed in the FDA's *Postapproval Pregnancy Safety Studies, Guidance for Industry Section B.10* [FDA 2019a], separate analyses will be performed for each pregnancy outcome. The primary analysis for major congenital malformations will be based on exposure to QUVIVIQ within 5 half-lives prior to conception or the first trimester [see Sections 5.7.1.3 and 5.7.4.4]. For the secondary outcomes, subgroup analyses based on the timing of exposure (preconception, first trimester, second trimester, third trimester) will be conducted as sample size permits. Consistent with prior research on sleep medications in pregnancy [Huitfeldt 2020, Lupattelli 2019, Calderon-Margalit 2009, Wang 2010], each outcome will be assessed with respect to exposure timing as outlined in this table.

Secondary outcome of interest	Exposure timing for evaluation in analyses	
Pregnancy complications		
Preeclampsia	Preconception, first trimester, second trimester, third trimester	
Pregnancy-induced hypertension	Preconception, first trimester, second trimester, third trimester	
Preterm labor	Preconception, first trimester, second trimester, third trimester	
Gestational diabetes	Preconception, first trimester, second trimester, third trimester	
Pregnancy outcomes		
Elective and therapeutic abortion	Preconception, first trimester, second trimester, third trimester	
Spontaneous abortion	Preconception, first trimester, second trimester	
Fetal death or stillbirth	Preconception, first trimester, second trimester, third trimester	
Live birth	Preconception, first trimester, second trimester, third trimester	
Preterm birth	Preconception, first trimester, second trimester, third trimester	

Confidential

Infant outcomes		
Minor congenital	Preconception, first trimester, second trimester, third	
malformations	trimester	
Size for gestational age	Preconception, first trimester, second trimester, third trimester	
Infant death	Preconception, first trimester, second trimester, third trimester	
Hospitalization for serious	Preconception, first trimester, second trimester, third	
illness	trimester	
Postnatal growth and	Preconception, first trimester, second trimester, third	
development	trimester	

Preconception: within 5 half-lives prior to conception (LMP + 14 days), First trimester: conception to 13⁺⁶ weeks' gestation, Second trimester: 14⁺⁰ to 27⁺⁶ weeks' gestation, Third trimester: 28⁺⁰ weeks' gestation to end of pregnancy.

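### The main spontaneous-abortion comparison keeps women in the denominator who can no longer have the event, and deals with entry and exposure timing only in analyses that depend on sample size

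*Protocol*

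**What the plan says.** - **Estimator.** Section 5.7.4.2 obtains the prevalence of spontaneous abortion by "dividing the number of women with fetal loss occurring before 20 weeks gestation by the total number of pregnant women".
- **Comparison.** Section 5.7.4.3 sets every secondary outcome in Cohort A against B, B1 and B2 by risk ratio, with one-sided 97.5% intervals. Covariate adjustment may be explored. Gestational age at enrollment is not among the key covariates named there.
- **Entry.** Section 5.2.1.1 requires only this: "Pregnancy is ongoing and outcome of pregnancy (i.e., pregnancy loss or live birth) is not known". Section 5.2 asks for enrollment as soon as the pregnancy is known, "preferably in the first trimester before 20 weeks gestation", which is a preference and not a limit.
- **Exposure.** Section 5.3.1 defines Cohort A by "Exposure to QUVIVIQ at any point during the patient's pregnancy or at any time within 5 half-lives prior to conception".
- **Timing analyses.** Table 6 in section 5.7.4.4 has a spontaneous-abortion row for "Women in primary analysis based on gestational age of enrollment". All Table 6 analyses depend on sufficient sample size. Section 5.7.2.1 and Appendix 4 plan analyses by exposure window as sample size allows: "each outcome will be assessed with respect to exposure timing as outlined in this table". For spontaneous abortion the windows are preconception, first trimester and second trimester.
- **Acknowledged limitation.** Section 5.9.1.3 accepts that early losses before enrollment are missed and that the loss rate will be underestimated.

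**The concern.** Spontaneous abortion is a loss before 20 weeks. A woman who enrolls at 20 weeks or later has no chance of the event, yet she counts in the denominator. A woman who enrolls at 12 weeks has already passed much of the period at risk. A crude proportion treats both like a woman observed from week 5.

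There are two consequences. First, the Cohort A proportion, which is a secondary objective in section 4.2, is diluted even without a comparator. Section 5.9.1.3 mentions missed early losses but not women who are no longer at risk. Second, the risk ratios against B1, B2 and B mix any drug effect with differences in when women entered.

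Exposure timing adds a related problem. A woman first exposed at 15 weeks was necessarily event-free until then, and a pregnancy lost at 9 weeks had little time to become exposed, which matters most for A versus B2. In Appendix 4 the second-trimester window runs to 27+6 weeks, beyond the 20-week cut-off. It does not state that the pregnancy must be ongoing at the window's start or that exposure must precede the loss.

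A false miscarriage signal, or a hidden one, would be a serious error in a pregnancy safety registry.

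**Working it through.** **1. The protocol's own figure.** Table 4 gives power above 99.9% for spontaneous abortion at a risk ratio of 2.5, with P_B = 11.0%, P_A = 11.55% and margin 16.5 points. Its footnote bases this on all 785 enrolled women (204 A, 387 B1, 194 B2).

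Power = Φ((margin − (P_A − P_B))/SE − 1.96), with SE = √(v(1/n_A + 1/n_B)) and v = (0.11 × 0.89 + 0.1155 × 0.8845)/2 = 0.1000.

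- A vs B1: SE = 0.0274; 0.1595/0.0274 − 1.96 ≈ 3.87; power 99.99%.
- A vs B2: SE = 0.0317; about 3.07; power 99.89%.
- A vs B (581): SE = 0.0257; about 4.24; power above 99.99%.

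The figures reproduce to within 0.1 point. They apply the full 11% to every enrolled woman, as if all were observed from early pregnancy.

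**2. Women not at risk.** Let f be the share enrolled at or after 20 weeks. The cohort proportion is multiplied by (1 − f), so 11% becomes 9.9% at f = 10% and 8.8% at f = 20%. If risk among earlier entrants is equal, the crude ratio is (1 − f_A)/(1 − f_B1):

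- 0% vs 10%: 1/0.90 = 1.11
- 0% vs 20%: 1/0.80 = 1.25
- 10% vs 30%: 0.90/0.70 = 1.29

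The values of f are assumed.

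**3. Entry before 20 weeks, no drug effect.** The 11% is from Table 4. The start at week 5 and the hazard shape are assumptions. Weekly hazard h_w = k × 0.5^((w−5)/H) for w = 5 to 19, with k chosen so that 1 − exp(−Σh_w) = 0.11. Residual risk at entry week g is R(g) = 1 − exp(−Σ_{w≥g} h_w).

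| Hazard | R(8) | R(10) | Ratio, week 8 vs 10 | Ratio, one-week shift |
|---|---|---|---|---|
| Halves every 2 weeks | 4.00% | 1.99% | 2.01 | 1.41 |
| Halves every 3 weeks | 5.48% | 3.36% | 1.63 | 1.28 |
| Halves every 4 weeks | 6.34% | 4.26% | 1.49 | 1.22 |
| Flat | 8.90% | 7.47% | 1.19 | 1.10 |

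The last column compares an assumed entry distribution (week 6: 20%, 8: 30%, 10: 20%, 12: 15%, 16: 10%, 22: 5%) with the same distribution one week later. If Cohort A is the later one, the ratios invert: week 10 versus 8 gives 1/2.01 = 0.50 to 1/1.19 = 0.84. With equal entry the ratio is 1.0.

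**4. Masking.** Suppose the hazard in A is truly doubled, A enters at week 10 and the comparator at week 8. The apparent ratio, (1 − exp(−2Σ_{w≥10} h_w))/R(8), is 0.98, 1.20 and 1.32 for halving times of 2, 3 and 4 weeks, and 1.62 for a flat hazard.

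**The case against.** **The plan does not ignore timing.** A reader might infer that nothing allows for entry or exposure timing. That is too strong. Table 6 names spontaneous abortion by gestational age at enrollment, Appendix 4 lists outcome-specific windows and omits the third trimester for this outcome, and section 5.9.1.2 stratifies outcomes by enrollment relative to receipt of prenatal test results. What remains is that the first two depend on sample size and the third is not a gestational-age analysis. The Table 6 row is also confined to women in the primary analysis, which compares A with B1 and so, on its face, does not reach B2 or B overall.

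**Recruitment is meant to be aligned.** Sections 5.4.5 and 5.9.2 ask for early referral to both cohorts through the same centers and strategies, and section 5.1 applies the same procedures. This may narrow the gap in entry but does not ensure equality, and the estimator makes no correction if a gap remains.

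**Section 5.9.1.3.** The sentence "There is no reason to believe that this study will be differentially impacted by this bias" might be read as claiming equal bias across A, B1 and B2. It goes on to conclude about the relative rate compared with other registries. On the internal comparison the section is silent, not wrong.

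**Size.** Larger ratios can be produced. Comparing the entry distribution above with an assumed later one (week 8: 10%, 10: 20%, 12: 20%, 16: 20%, 22: 30%) gives 2.3 to 3.3 under the declining hazards. That rests on mean entry of 10.1 versus 15.0 weeks, a gap nothing in the protocol supports. Even there the absolute bias is 2.3 to 2.9 points, far below Table 4's smallest margin of 16.5 points. A conclusion based on the difference and that margin is therefore little affected. The risk ratio and its interval are.

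**Deferral to the SAP.** Risk-set rules for windows are ordinary SAP content, and Appendix 4 does not say that exposure after the outcome counts. Third-trimester exposure is listed for elective and therapeutic abortion, which has no gestational limit, so it says nothing about spontaneous abortion. However, the crude denominator is fixed in the protocol itself.

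**Conclusion.** The point holds for the main analysis. Followed as written, section 5.7.4.2 keeps women in the denominator who cannot have the event and gives late entrants the same weight as women observed from early pregnancy. The Cohort A proportion is diluted in proportion to the share enrolled at or after 20 weeks. The risk ratios against B1, B2 and B are biased, in either direction, to the extent that entry or exposure timing differs between cohorts.

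Whether it differs, and by how much, cannot be known from the protocol. Under no drug effect and the assumed hazards, a one-week shift produces an apparent ratio of about 1.1 to 1.4, and week 8 versus week 10 about 1.2 to 2.0. These are illustrations, not predictions. The outcome is secondary but is a key safety measure, and the correction is cheap, so the change should be made.

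**What to change.** - **Section 5.7.4.2.** Restrict the spontaneous-abortion risk set to pregnancies enrolled before 20+0 weeks. Make the main comparison a left-truncated (delayed-entry) analysis on gestational age from enrollment, with elective termination as a censoring or competing event. Count exposure only from its start date and before the outcome. Keep the crude proportion as a descriptive figure.
- **Section 5.7.4.4, Table 6.** Make the analysis by gestational age at entry unconditional.
- **Appendix 4.** For the spontaneous-abortion windows, compare exposed women with pregnancies still ongoing at the window's start.
- **Section 5.9.1.3.** Keep the sentence about other registries and add that gestational age at entry may differ between Cohorts A, B1 and B2.

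The cost is protocol and SAP wording and modest programming. The date of the last menstrual period, gestational age at enrollment, and medication start and stop dates are already collected under section 5.3.3.1. Late enrollees leave this one endpoint, so its interval widens slightly.
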